## **8.5. Treatment Phase**

The treatment phase begins from the time study drug is first administered (Day 1 of Cycle 1), and continues until the subject discontinues study treatment. Each cycle during the treatment period will consist of 28 days and will be denoted numerically (Cycle 1, Cycle 2, etc.).

After the initial 2 cycles of therapy, study visits will occur on Day 1 of each cycle for Cycles 3 to 7, then every 3 cycles thereafter (i.e., Day 1 of Cycle 10, 13, etc.) as long as the subject continues to receive study drug. The modified dosing schedule for AEs is described in [Table 4](#).

Response assessments, as defined in [Section 7](#), will be performed according to the Schedule of Assessments ([Appendix 1](#)) and detailed in [Appendix 5](#). The disease/response assessment will be performed every 2 months ( $\pm 7$  days) for the first 6 months on study, every 3 months ( $\pm 7$  days) during the following 12 months, and every 6 months ( $\pm 14$  days) thereafter.

For those subjects who switch to CS after disease progression on IS, the date of PD will be designated as a new baseline, and subsequent response assessments will be scheduled per the protocol-specified frequency using the new baseline date and CT scan for reference.

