### 11.2.2. Statistical Analyses

The primary analysis of ORR for FL will be triggered after all 91 subjects in the PEP enrolled in the study (except those who discontinue early) have been followed for at least 6 months from the start of study drug.

The final analysis of DOR for FL will be triggered after most responders in the Primary Efficacy Population have a minimum of 12 months of follow-up from first response.

The final analysis of ORR and DOR for MZL will be triggered after most of the responders in the MZL ITT population (except those who discontinue early) have been followed for at least 12 months from first response.

Summary statistics for continuous variables will include the mean, standard deviation, median, and range (minimum/maximum). Categorical variables will be presented as frequency counts and percentages. Time-to-event variables will be summarized using Kaplan-Meier (KM) methods (median, 95% CI, number of events, number censored, KM figures). Data listings will be created to support each table and to present all data.

The efficacy analysis of ORR for MZL as determined by the IRRC will be based on the ITT MZL Population, utilizing the best overall ORR prior to first PD. The CR rate as determined by the IRRC will be reported similarly. The ORR as determined by the IRRC in the EE Population will be reported as a sensitivity analysis.

Secondary efficacy endpoints including DOR, DORR, PFS, TTF, time to recapture of response (as assessed by the IRRC and/or Investigator); and overall survival (OS) will be summarized using KM summary statistics for the ITT IS FL Population and ITT MZL Population respectively.

Similarly, the efficacy endpoints based on Investigator assessments will be summarized as supportive analyses.

Safety analyses will be performed on the Safety Population, as defined in [Section 11.2.1](#).

Overall summary of safety will include but not limited to the following analyses:

- TEAEs, including severity and possible relationship to study drug and/or study treatment
- AESIs
- treatment-emergent SAEs
- discontinuations from study treatment due to AEs
- treatment-emergent abnormal changes in laboratory values
- treatment-emergent abnormal changes in vital signs.

The rate of AESIs and the respective 95% CI will be calculated by dosing group (CS and IS) and overall.

Time to AESIs will be calculated from the first day of study treatment to first occurrence of AESI, utilizing KM methodology.

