## 2.3. Brief Description

Under Protocol Amendment 2, this is a global, multicenter, open label, single-arm, phase 2 study of the PI3K $\delta$  inhibitor ME-401 (zandelisib) in subjects with relapsed/refractory FL or MZL. ME-401 will be administered orally at a dose of 60 mg given once a day in 28-day cycles, with the first day of treatment designated as Day 1. Treatment with ME-401 can be administered based on a continuous schedule (CS) or an intermittent schedule (IS).

[figure not shown]
The CS (or Group A in Protocol Amendment 1) includes daily dosing for the whole duration of a treatment cycle until protocol-defined criteria is met for treatment interruption, modification to intermittent dosing to manage toxicity, or discontinuation.

The IS (or Group B in Protocol Amendment 1) includes:

- continuous daily therapy for the initial 2 cycles (~56 days) of treatment
- the intermittent treatment begins at Cycle 3, with ME-401 administered daily for the first 7 days of every 28-day cycle (7 days on treatment and 21 days off treatment)

Under Protocol Amendment 1 (Figure 1a), subjects were randomized 1:1 to receive CS or IS. Since Protocol Amendment 2 (Figure 1b), the initial CS treatment arm was terminated, and all new subjects were enrolled to receive therapy on the IS only. If CS subjects already completed 2 initial cycles of therapy, they were switched to IS dosing after they complete therapy in the ongoing cycle of treatment, and if they had not completed the first 2 cycles of therapy they were switched to IS dosing after completion of the first two cycles of therapy on CS. Subjects who progress on IS dosing may be switched to CS dosing. Subjects will continue to receive study drug in accordance with the IS dosing regimen (or CS dosing regimen if switched from IS after disease progression [PD]) until investigator-assessed disease progression or unmanageable toxicity requiring treatment discontinuation, subject's decision to withdraw their consent to participate on study, or study closure by the Sponsor.

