**Table 1: Schedule of Assessments (Amendment 4)**

Assessment/Procedure	Screening b	Cycle 1			Cycle 2		Cycle 3	Cycle 4		Cycle 5	Cycle 6		Cycle 7	Cycles 10, 13, 16, 19, 22, 25 d...	EOT/30-Day Safety Follow-up e	Post-Treatment Long-Term Follow-up
		1 c	8	15	1	15	1	1	7	1	1	7	1			
Day(s) of Cycle	-28 to -1	1 c	8	15	1	15	1	1	7	1	1	7	1	1	30 (± 3) days post last dose or treatment discontinuation	Every 3 Months
Study Day(s)	-28 to -1	1	8	15	29	43	57	85	91	113	141	147	169	253, 337, 421, 505, 589...		
Visit Window (days) a			±3	±3	±7	±7	±7	±7	±7	±7	±7	±7	±7	±7 a		
Informed consent form (ICF)	X															
Medical history f	X															
Physical examination	X	X			X		X	X		X	X		X	X	X	
Symptom-directed exam g			X	X		X										
Vital signs h	X	X	X	X	X	X	X	X		X	X		X	X	X	
Height	X															
Weight	X	X			X		X	X		X	X		X	X	X	
ECOG performance status	X	X			X		X	X		X	X		X	X	X	
Pregnancy test i	X	X			X		X	X		X	X		X	X	X	
HIV testing j	X															
Hepatitis B and C testing k	X															
Adverse events l		X	X	X	X	X	X	X		X	X		X	X	X	
Concomitant medication m	X	X	X	X	X	X	X	X		X	X		X	X	X	
ECG n	X	X					X				X			X	X	
CBC with differential o	X	X	X	X	X	X	X	X		X	X		X	X	X	
Serum chemistry p	X	X	X	X	X	X	X	X		X	X		X	X	X	
Coagulation q	X	X			X		X			X			X	X	X	
PCR test for CMV	X	X			X		X	X		X	X		X	X		
Urinalysis (Dipstick) r	X	X			X		X	X		X	X		X	X	X	

Assessment/Procedure	Screening b	Cycle 1			Cycle 2		Cycle 3	Cycle 4		Cycle 5	Cycle 6		Cycle 7	Cycles 10, 13, 16, 19, 22, 25 d ...	EOT/30-Day Safety Follow-up e	Post-Treatment Long-Term Follow-up
		1 c	8	15	1	15	1	1	7	1	1	7	1			
Day(s) of Cycle	-28 to -1	1 c	8	15	1	15	1	1	7	1	1	7	1	1	30 (± 3) days post last dose or treatment discontinuation	Every 3 Months
Study Day(s)	-28 to -1	1	8	15	29	43	57	85	91	113	141	147	169	253, 337, 421, 505, 589...		
Visit Window (days) a			±3	±3	±7	±7	±7	±7	±7	±7	±7	±7	±7	±7 a		
COVID-19 test s	X															
Issue and assess compliance diary t		X			X		X	X		X	X		X	X		
Dispense study drug u		X			X		X	X		X	X		X	X		
PK Sampling v		X		X w	X				X			X				
Echocardiogram or MUGA x	X														X	

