Correlative immune study (pre-dose) y		X		X	X		X			X			X	X	X	
Opportunistic infection monitoring z		X			X		X	X		X	X		X	X	X	
Post-Treatment Follow-up procedures aa																X

Response Assessment bb,cc	Screening	Every 2 Months for the First 6 Months			Every 3 Months for the Next 12 Months (through 18 Months)				Every 6 Months Thereafter
		61	121	182	274	365	456	547	
Study Day		61	121	182	274	365	456	547	730, 912, 1095...
Visit Window (days)		±7	±7	±7	±7	±7	±7	±7	±14
CT neck/chest/abdomen/pelvis dd	X	X	X	X	X	X	X	X	X
FDG-PET scan ee	X		X			X			
Bone marrow biopsy/aspirate ff						X			
Endoscopy with biopsy gg						X			

Abbreviations: ALP = alkaline phosphatase; ALT = alanine aminotransferase; ANC = absolute neutrophil count; aPTT = activated partial thromboplastin time; AST = aspartate aminotransferase; BP = blood pressure; BUN = blood urea nitrogen; CBC = complete blood count; CMV = cytomegalovirus; CMR = complete metabolic response; CO2 = carbon dioxide; CR = complete response; CT = computed tomography; ECG = electrocardiogram; ECOG = Eastern Cooperative Oncology Group; EOT = end of treatment; FDG-PET = 18F-fluorodeoxyglucose positron emission tomography; HcT = hematocrit; HGB = hemoglobin; HIV = human immunodeficiency virus; HR = heart rate; ICF = informed consent form; INR = international normalized ratio; LDH = lactate dehydrogenase; MCH = mean corpuscular hemoglobin; MUGA = multigated acquisition scan; PCR = polymerase chain reaction; PK = pharmacokinetic; PT = prothrombin time; RBC = red blood cell; SOC = standard of care; WBC = white blood cell.

- a. **Study Assessment Day(s)** – There is ±3-day window allowable for each clinic visit for Cycle 1 Day 8 and Cycle 1 Day 15. For Cycles 2 through 25, the allowable window is ±7 days. After Cycle 25, the allowable window is ±1 month for each clinic visit and its associated assessments.

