- u. **Dispense Study Drug** – Study drug is to be taken orally once a day on an empty stomach at least 1 hour prior to food intake or 2 hours after food intake at the same time each day. On days of PK sampling, instruct subjects to not take study drug until after the pre-dose PK sample is drawn. Compliance diary and count of returned capsules are performed on each day of dispensing study drug.
- v. **PK sampling** – Pre-dose PK samples are to be obtained within 1 hour before study drug administration on Cycle 1 Day 1, Cycle 2 Day 1, Cycle 4 Day 7, and Cycle 6 Day 7. Pre-dose PK samples collected after Cycle 1 Day 1 are to be obtained within  $\pm 60$  minutes of the scheduled time, which is based on the Cycle 1 Day 1 dosing time.
- w. **PK Sampling – Cycle 1 Day 15** – pre-dose and 3 hours ( $\pm 30$  min) post intake of study drug. Collect data regarding food and drink intake 4 hours prior to study drug intake.
- x. **Echocardiogram or MUGA** – Performed at screening, EOT/30-Day Safety Follow-up visit, and as clinically indicated. The same methodology (echocardiogram or MUGA) should be used throughout the study.
- y. **Correlative Sample Study** – US Sites only. Samples will be obtained pre-dose on Day 1 of Cycle 1, and then pre-dose on the following visits: Day 15 of Cycle 1; Day 1 of Cycles 2, 3, 5, 7, 10; then every 3 cycles thereafter; and at the EOT/30-Day Safety Follow-up visit. Fresh blood samples will be collected and shipped overnight to a central laboratory for analysis. Samples may be shipped only Monday to Thursday. Samples may not be shipped for delivery on weekends or holidays. If possible, a sample will also be obtained when a subject develops a late onset Grade 2 AE of diarrhea/colitis, rash/mucositis, transaminase elevation, or non-infectious pneumonitis, or when a subject discontinues study drug permanently for another reason. Samples will be collected at the first visit of the adverse event, at the time when treatment is held, and at the time when treatment is resumed.

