#### **8.4. Laboratory Evaluations**

Lab evaluations will include hematology (including coagulation), serum chemistry, urinalysis, pregnancy test, HIV testing, Hepatitis B and Hepatitis C testing, bone marrow aspiration/biopsy, PCR tests for CMV and opportunistic infection (OI) monitoring.

For statistical and graphical summaries of the laboratory tests, values below or above the limit of detection (e.g., '< 3' or '>500') are substituted with the lower limit of detection minus 1% for values below the lower limit and are substituted with the upper limit of detection plus 1% for values above the upper limit (e.g., '< 3' is substituted by '2.97', '> 500' is substituted by '505'). In data listings, the values are shown including the < or > sign.

Results from the hematology, chemistry, and urinalysis will be summarized by visit using descriptive statistics, including the observed values and change from baseline values for numeric parameters and distribution of categories for categorical parameters. Boxplots by visit will be generated for selected hematology/chemistry parameters.

In addition, the incidence rate of grade 3 and above toxicity for selected hematology and chemistry parameters will be summarized by visit. Separate listings will be produced for subjects with grade 3 and above toxicity for selected hematology and chemistry parameters.

Treatment-emergent toxicities are defined as the worsening of lab toxicity grade comparing to the baseline. The incidence rate of treatment-emergent grade 3 and above toxicity for hematology and chemistry parameters will be summarized by visit.

By-subject listings of hematology, serum chemistry, and urinalysis tests, including lab normal ranges, will be provided. Derived CTCAE grades will be included in listings, as applicable.

The following lab data will be listed only: pregnancy test, HIV, Hepatitis B and Hepatitis C tests, bone marrow aspiration/biopsy, CMV titers, and OI monitoring.

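### From Cycle 4, scheduled chemistry and blood counts are drawn off drug on the intermittent schedule but on drug on the continuous schedule, so the descriptive CS/IS comparison of AST/ALT and laboratory toxicity may be biased toward the IS

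*SAP*

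**What the plan says.** **Dosing.** SAP 2.3 gives daily drug for two 28-day cycles and then, from Cycle 3, drug "administered daily for the first 7 days of every 28-day cycle (7 days on treatment and 21 days off treatment".

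**Sampling.** Protocol 8.5 says that after the first two cycles "study visits will occur on Day 1 of each cycle for Cycles 3 to 7, then every 3 cycles thereafter". In Protocol Appendix 1 and SAP Table 1, the blood count and serum chemistry rows are marked on Cycle 1 Days 1, 8 and 15, on Cycle 2 Days 1 and 15, on Day 1 of Cycles 3 to 7, 10, 13 and so on, and at the end-of-treatment visit 30 (±3) days after the last dose. Both rows are blank at Cycle 4 Day 7 and Cycle 6 Day 7. Only the PK row is marked there; its footnote lists pre-dose samples on Cycle 1 Day 1, "Cycle 2 Day 1, Cycle 4 Day 7, and Cycle 6 Day 7". On timing, the same table says: "For Cycles 2 through 25, the allowable window is ±7 days".

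**Reporting.** Protocol 11.2.2: "The rate of AESIs and the respective 95% CI will be calculated by dosing group (CS and IS) and overall". SAP 5.1 presents safety by actual schedule, and SAP 8.3.4 presents time to AESI by dosing group. SAP 8.4: "The incidence rate of treatment-emergent grade 3 and above toxicity for hematology and chemistry parameters will be summarized by visit". SAP 5.1 keeps unscheduled and repeat measurements out of summary tables unless specified otherwise. AST/ALT of Grade 2 or higher is an AESI (Protocol 5.3.2, SAP 8.3.2); cytopenias are not on that list.

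**The concern.** An AST/ALT rise without symptoms is usually found only by a blood test. On the IS, no scheduled test falls inside a 7-day dosing block or in the two weeks after it. Protocol 1.6.2.3 builds the three-week break as about one week of wash-out and two weeks of regulatory T-cell recovery, and Protocol 2.3 names transaminase increases among the toxicities that intermittent dosing is meant to mitigate. The scheduled sample is thus taken when recovery is expected to be most complete. On the CS, the same calendar day is a dosing day.

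At stake is what can be concluded about IS safety. A lower AST/ALT rate or a longer time to AESI on the IS could reflect the schedule, the sampling time, or both, and nothing in the SAP separates them. The weekly ALT/AST and blood-count checks in Protocol Table 4 begin only after a graded abnormality is known, so they do not fill the gap. A peak that an extra test does catch may still be left out of the by-visit laboratory tables.

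**Working it through.** **1. The plan's nearest figure.** The documents give no number for this point. The closest figure that depends on AESI counts is the precision statement in SAP 2.4: at most 15 of 120 IS FL subjects with a Grade ≥3 AESI. The exact two-sided 95% Clopper-Pearson interval for 15/120 = 12.5% is 7.2–19.8%, as stated. For 16/120 = 13.3% it is 7.8–20.7%, which no longer excludes 20%. The rule has no slack, so at the boundary a single unrecorded Grade ≥3 event of any AESI type would matter.

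**2. Drug-free time before each draw (IS, planned calendar).**
- Post-baseline draws through Cycle 3 Day 1 (study days 8, 15, 29, 43, 57): 5 draws. All follow daily dosing and are on drug in both groups.
- From Cycle 4 (study days 85, 113, 141, 169, 253, 337 and on): the last dose is on Day 7 and the next cycle's Day 1 is Day 29 of the same count. 29 − 7 = 22 days since the last dose, or 21 full drug-free days.
- With the ±7-day window: 14 to 28 drug-free days, or 15 to 29 days since the last dose. This takes the next block to start at or after the visit, where drug is dispensed.
- At the 28-hour half-life in Protocol 1.5: 22 × 24 / 28 = 18.9 half-lives. This describes drug in plasma, not recovery of the liver or marrow.
- Scheduled on-drug draws from Cycle 4: 0 on the IS. With panels at the two Day 7 visits: 2.
- The end-of-treatment draw is off drug in both groups.

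**3. What a scheduled draw can see.** The documents give no recovery time, so persistence after the Day 7 dose is an assumption. An abnormality lasting D days is seen at visit offset w (−7 to +7 days) if 22 + w ≤ D.

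| D (days after last dose) | Seen at nominal Day 1? | Offsets at which seen |
|---|---|---|
| 14 or less | no | 0 of 15 |
| 17 | no | 3 of 15 |
| 21 | no | 7 of 15 |
| 24 | yes | 10 of 15 |
| 28 | yes | 14 of 15 |
| 29 or more | yes | 15 of 15 |

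**4. An illustration in terms of peak height.** Assume the rise peaks at the last dose and falls exponentially with half-time h. To be still above 3 × ULN at 22 days, the peak must exceed 3 × 2^(22/h): 63 × ULN for h = 5 days, 26 for h = 7, 14 for h = 10 and 9 for h = 14. A delayed immune-mediated rise need not follow this shape.

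**5. A gap common to both schedules.** After Cycle 7, draws come every 12 weeks, so two of every three cycles have no draw on the next Day 1. This applies to the CS as well.

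**The case against.** The case against is substantial, and much of it stands.

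- **No result is shown.** A reader might infer that hepatic AESI rates do favour the IS because of sampling. The documents contain no CS/IS hepatic result for this study and no AST/ALT time course. In the Phase 1b study, all-grade AST increase was nearly equal, 8/39 (20.5%) on the CS and 11/57 (19.3%) on the IS (Protocol Table 2). That study's draw days are not given, so this neither supports nor refutes the point. Only the direction of a possible bias follows.
- **The comparison is descriptive.** The CS arm was closed with Amendment 2 and its subjects moved to the IS. The stated objectives concern the IS, and no CS/IS test is planned. This limits the consequence, but the rates, intervals and Kaplan-Meier curves by schedule are still to be produced.
- **Both groups share on-drug draws through Cycle 3 Day 1**, and AESIs can also come from symptom-led tests. Correct; the gap is confined to later asymptomatic events.
- **Table 4.** A reader might infer that the toxicity rules are disabled. That goes too far. Table 4 leaves dosing unchanged for Grade 2 ALT/AST. For a first Grade 3 rise that clears within the cycle, Protocol 5.3.1 has the subject complete the planned days off and resume on the next Day 1. Recognition matters mainly for Grade 4 or recurrent Grade 3.
- **By-visit laboratory tables already show the periods.** True for those tables, but not for AESI rates or time to AESI.
- **Enrollment is closed** (Protocol 8.3), so extra Day 7 panels can reach only subjects not yet at those visits.

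**Conclusion.** The point holds as a limit on interpretation. From Cycle 4, scheduled chemistry and blood counts on the IS are off drug, and those of subjects dosed on the CS are not. Short-lived, asymptomatic abnormalities after a dosing block can therefore be missed on the IS alone. CS/IS displays of AST/ALT AESIs, time to AESI and by-visit Grade ≥3 laboratory toxicity may be biased toward the IS.

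The size cannot be derived from the documents. At the nominal visit it is zero for abnormalities lasting 22 days or more after the last dose. For those lasting 14 days or less, no scheduled draw from Cycle 4 would find them. Between these limits it depends on how early the visit falls. This rests on the planned calendar and on the window being used as written.

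Two stronger readings are not supported: that the IS hepatic advantage is an artefact, and that cytopenias distort the AESI rate. Cytopenias are not AESIs, so that part bears only on the laboratory and cytopenia tables.

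**What to change.** 1. **SAP 8.3.2 to 8.3.4 and 8.4.** Report AST/ALT AESIs and worst Grade ≥3 laboratory toxicity separately for the period through Cycle 3 Day 1, when both groups are sampled on drug, and for the period afterwards. Include unscheduled values in the worst-grade summary. State that scheduled IS values from Cycle 4 are off drug and that a later CS/IS difference will not be read as an effect of the schedule. Cost: SAP wording, programming and one table split; no new data.
2. **Protocol Appendix 1 and SAP Table 1.** For subjects who have not yet reached them, mark blood count and serum chemistry at the existing Cycle 4 Day 7 and Cycle 6 Day 7 blood draws (study days 91 and 147). Cost: up to two local panels per remaining subject and no new visit. The documents do not say how many subjects remain, so the yield may be small or nil; change 1 does not depend on it.

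Both changes concern ascertainment and reporting. No dose or treatment rule is proposed.

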**Figure 1a: Study Schema (Protocol Amendment 1)**

[figure not shown]

Abbreviations: AERDM = AEs requiring dose modification or drug discontinuation; Rand = randomization.

a For subjects who require study drug interruption to manage ME-401 related toxicity or have disease progression.

b Safety follow up will occur 30 days (±3 days) from the last day of study drug treatment. Post-treatment follow-up will be conducted every 3 months to obtain data regarding disease progression, improvement in disease response, start of subsequent lymphoma therapy and death.

**Figure 1b: Study Schema (Protocol Amendments 2 and 3)**

Abbreviations: EOT = End of Treatment; FU = follow up; PD = progressive disease.

a Screening from Day -28 to Day -1.

b IS dosing schedule: 60 mg daily for the first 2 cycles (56 days) followed by 60 mg daily for 7 days of every 28-day cycle (7 days on / 21 days off treatment).

c Follow-up Period will include: 1) EOT/30-Day Safety Follow-up visit will occur 30 ( $\pm 3$ ) days from the last day of study drug treatment. 2) Efficacy Follow-up - for subjects who discontinue study treatment due to reasons other than disease progression or death, response follow up will occur until PD of the start of a new anti-cancer therapy. 3) Survival Follow-up visits will occur every 3 months until death, and will continue for up to 3 years after the last subject was enrolled in the study.

d Response assessments will be performed every 2 months ( $\pm 7$  days) for the first 6 months of therapy, every 3 months ( $\pm 7$  days) during the following 12 months, and every 6 months ( $\pm 14$  days) thereafter (starting with month 18).

Subjects who discontinue study drug will remain in the study with follow-up conducted every 3 months from the last dose of study drug to obtain post-treatment long-term follow-up information on disease status (i.e., change in disease response, progression), start of subsequent therapy, and survival (death). During this post-treatment follow-up phase, all subjects who discontinued treatment due to reasons other than PD must continue imaging tests to assess disease status, performed per the original protocol-defined schedule for disease/response assessment, or earlier if clinically indicated. Imaging test results will no longer be collected when a subject starts a new therapy or disease progression occurs and is documented in the post-treatment long-term follow-up phase. Survival follow-up will continue for up to 3 years after the last subject is enrolled in the study.

Individual subject participation in the study will include 28 days for screening, approximately 18 months of dosing with study drug, and follow-up for survival after discontinuation of study drug. Actual subject participation in the study may be shorter or longer depending on disease response, tolerability to therapy, and duration of long-term follow-up. The study will continue until all enrolled subjects (except those who discontinue early) have been followed for at least 6 months from the start of study drug.

